13.3 Analysis of Primary and Secondary Endpoints

The primary and secondary analyses will include all eligible patients who completed at least one cycle of dosing. The exception to this includes the planned analysis of toxicity data, which will include all patients who received study drug regardless of eligibility and regardless of whether they completed a full cycle. Progression-free rate will be estimated as binomial proportion and overall survival and progression-free survival estimates and curves will be generated using the Kaplan-Meier method.

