11.1.1 Definitions

Evaluable for Target Disease response. Only those participants who have measurable disease present at baseline, have received at least one cycle of therapy, and have had their disease re-evaluated will be considered evaluable for target disease response. These participants will have their response classified according to the definitions stated below. (Note: Participants who exhibit objective disease progression prior to the end of cycle 1 will also be considered evaluable.)

Evaluable Non-Target Disease Response. Participants who have lesions present at baseline that are evaluable but do not meet the definitions of measurable disease, have received at least one cycle of therapy, and have had their disease re-evaluated will be considered evaluable for non-target disease. The response assessment is based on the presence, absence, or unequivocal progression of the lesions.

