13. STATISTICAL CONSIDERATIONS

This is a three-arm phase II study exploring the anti-tumor activity of prexasertib (LY2606368) in patients with advanced cancer exhibiting either replicative stress, HR deficiency, or *CCNE1* amplification. The primary goal of the study will be to examine the progression-free rate at 4 months in all arms separately. Secondary efficacy measures will include assessment of objective response rate by RECIST 1.1 as well as toxicity using CTCAE version 4.0 criteria, overall survival (OS), and progression free survival (PFS).

Each arm will be conducted as a Simon's 2-stage design and will initially enroll 9 participants. If there are less than 2 subjects that are alive and progression-free at 4 months after initiation of prexasertib, that arm will be terminated. If 2 or more subjects are progression free by 4 months, then enrollment for that arm will be expanded to 19 subjects. A minimum of 6 patients must be alive and progression-free at 4 months for the cohort to be considered meaningful for further evaluation. If at any point a participant does not complete Cycle 1 dosing of the study agent, that participant may be replaced at the principal investigator's discretion.

Progression status by 4 months will be determined for all patients. We expect all patients to have this status documented. PFS will be defined as the time from study registration to documented disease progression per RECIST 1.1 criteria or death from any cause, whichever occurs first. OS will be defined as the time from study registration until death. Patients who have not experienced an event of interest by the time of analysis will be censored at the date they are last known to be progression-free for PFS and alive for OS.

This design provides 80% power to detect a progression-free rate at 4 months of 40% tested against a historical control rate of $\leq 15\%$ ⁵⁷ using a one-sided significance of 0.05.

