13.2 Sample Size, Accrual Rate and Study Duration

The planned sample size is a maximum of 19 patients in each arm. The replicative stress cohort is now closed and will not expand, having enrolled 10 participants. Allowing for replacement of participants who do not make it through one cycle of dosing, the estimate for the maximum sample size is 50 participants (with 35 yet to enroll as of 5 December 2017).

As of 5 December 2017, a total of 15 participants have been accrued. Adjusting for the current accrual level and slower estimated accrual for the *CCNE1* cohort, we anticipate accruing approximately 3-4 patients per quarter. An additional year of follow-up will be required on the last participant accrued to observe the patient’s response following study therapy, for a total study length of about 4.5 years. Participants will be identified via targeted NextGen sequencing using the DFCI/BWH OncoPanel or another CLIA-certified method for genotyping.

Table 13: Accrual Targets			
Ethnic Category	Sex/Gender		
	Females	Males	Total
Hispanic or Latino	3	+ 0	= 3

Not Hispanic or Latino	25	+	22	=	47
Ethnic Category: Total of all subjects	28	+	22	=	50
Racial Category					
American Indian or Alaskan Native	0	+	0	=	0
Asian	0	+	0	=	0
Black or African American	2	+	0	=	2
Native Hawaiian or other Pacific Islander	0	+	0	=	0
White	26	+	22	=	48
Racial Category: Total of all subjects	28	+	22	=	50

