13.5.2 Evaluation of the Primary Efficacy Endpoint

All eligible participants included in the study who complete at least one cycle of dosing will be assessed for response, even if there are major protocol therapy deviations. Each participant should be assigned one of the following categories: 1) complete response, 2) partial response, 3) stable disease, 4) progressive disease, 5) early death from malignant disease, 6) early death from toxicity, 7) early death because of other cause, or 9) unknown (not assessable, insufficient data). By arbitrary convention, category 9 usually designates the "unknown" status of any type of data in a clinical database.

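### Efficacy analyses drop patients who do not complete cycle 1, which inflates the 4-month rate, PFS and OS if they do worse; discretionary replacement can also push alpha above 0.05

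*Combined protocol and SAP*

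**What the plan says.** - **Analysis set.** Section 13.3: "The primary and secondary analyses will include all eligible patients who completed at least one cycle of dosing". Only toxicity is analysed in everyone who received drug. Section 13.5.2, on the primary efficacy endpoint, repeats the limit: "All eligible participants included in the study who complete at least one cycle of dosing will be assessed for response".
- **Replacement.** Section 13 says that a participant who "does not complete Cycle 1 dosing of the study agent, that participant may be replaced at the principal" investigator's discretion. Section 13.2 sizes the study for this: "Allowing for replacement of participants who do not make it through one cycle of dosing, the estimate for the maximum sample size is 50" participants.
- **Design.** Each arm is a Simon two-stage design. It continues with at least 2 successes in 9 and is declared worth pursuing with at least 6 in 19. Section 13: "This design provides 80% power to detect a progression-free rate at 4 months of 40% tested against a historical control rate of" at most 15%, one-sided 0.05.
- **Endpoints.** The primary endpoint is the proportion alive and progression-free at 4 months (1.2, 13). PFS and OS run from registration (11.1.5, 13).
- **Text pointing the other way.** Section 13: "Progression status by 4 months will be determined for all patients". Section 11.1.1, on target disease response: "Participants who exhibit objective disease progression prior to the end of cycle 1 will also be considered evaluable". Section 13.5.2 includes among its outcome categories "early death from malignant disease, 6) early death from toxicity, 7) early death because of other cause".

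**The concern.** Whether a patient enters the efficacy set depends on something that happens after registration and is plausibly tied to outcome. Section 5.5 lists progression, intercurrent illness and unacceptable adverse events among the reasons for stopping therapy. A patient who dies or progresses before completing cycle 1 is a known failure on the primary endpoint and an event for PFS (for OS, if the event is death), but is removed.

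Exclusion and replacement act differently. Exclusion is a fixed rule that affects the estimates. Replacement is optional and affects the decision rule, because each replaced failure gives the arm another chance of a success while the cut-offs of 2 and 6 stay the same.

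The boundary is also loose. Completing a cycle of dosing is not defined. Under 6.3.1 cycle days keep counting when a dose is held, so a patient whose day 15 dose is held could be classed either way. In an open-label trial with arms of 9 and 19, one or two such classifications can change a go/no-go decision.

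**Working it through.** **1. The plan's own figures.** Inputs from Section 13: n1 = 9, continue if X1 ≥ 2; n = 19, success if the total is ≥ 6; p0 = 0.15, p1 = 0.40.

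P(success | p) = Σ over x = 2 to 9 of Bin(9, x; p) × P(Bin(10, p) ≥ 6 − x)

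- At p = 0.15: alpha = 0.0497; probability of stopping at stage 1 = 0.599.
- At p = 0.40: power = 0.813.

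The stated design is reproduced, with 0.0003 of alpha to spare.

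**2. Effect of exclusion on the estimate.** Assumptions, since the documents give neither figure: q = share of treated patients not completing cycle 1; g = their 4-month success rate. With p the rate in all treated patients:

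rate in completers = (p − qg)/(1 − q)

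| | q = 5% | q = 10% | q = 20% |
|---|---|---|---|
| p = 15%, g = 0 | 15.8% | 16.7% | 18.8% |
| p = 40%, g = 0 | 42.1% | 44.4% | 50.0% |

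At q = 10%, a true 15% reads as 16.1% with g = 5%, 15.6% with g = 10% and 15.0% with g = 15%. As a count, 5 successes with 2 of 19 patients excluded reads 5/17 = 29% instead of 5/19 = 26%. Exclusion without replacement, with the cut-offs kept, does not raise alpha.

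**3. Room for replacement.** The replicative stress arm closed at 10 (13.2). 10 + 19 + 19 = 48, so the estimated maximum of 50 leaves 2 if both other arms fill. If one of them stops at 9, 50 − (10 + 9 + 19) = 12.

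**4. Effect of replacement on alpha.** Exact recursion over slots filled, successes and replacements left. At each enrolment the patient is a completer success with probability p − qg, a non-completer with probability q, and otherwise a completer failure. Non-completers are replaced while replacements remain. With p = 0.15 in all treated patients and g = 0:

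| Replacements allowed in the arm | q = 5% | q = 10% | q = 20% |
|---|---|---|---|
| 0 | 0.0497 | 0.0497 | 0.0497 |
| 1 | 0.057 | 0.061 | 0.063 |
| 2 | 0.060 | 0.068 | 0.077 |
| 12 | 0.062 | 0.077 | 0.120 |

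The 0.120 is an extreme case: q = 20%, every non-completer a failure, and the other open arm stopped at 9.

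With g > 0 the result depends on how non-completers left unreplaced are handled: (A) they fill a slot without a success, or (B) they are counted by true outcome. Alpha at q = 5/10/20%:

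| | g = 5% | g = 10% | g = 15% |
|---|---|---|---|
| 1 replacement, A | 0.053/0.053/0.047 | 0.050/0.046/0.035 | 0.046/0.039/0.024 |
| 1 replacement, B | 0.055/0.057/0.058 | 0.052/0.053/0.054 | 0.0497 |
| 2 replacements, A | 0.056/0.060/0.058 | 0.052/0.052/0.042 | 0.049/0.044/0.030 |
| 2 replacements, B | 0.057/0.062/0.067 | 0.053/0.056/0.058 | 0.0497 |

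**5. If the 15% was measured in completers.** The all-treated null rate is then 0.15(1 − q) with g = 0. Alpha is 0.046/0.039/0.024 with one replacement and 0.049/0.044/0.030 with two, and never exceeds 0.0497.

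**6. Do the other passages rescue early failures?** No. Section 13 promises that 4-month status will be determined for everyone, but 13.3 decides who is analysed. The sentence in 11.1.1 concerns evaluability for target disease response. The early-death categories in 13.5.2 apply inside a set already limited to completers. The first restaging is at the end of cycle 2 (11.1), so for non-completers other than early deaths and documented early progressors, 4-month status is mostly unknown when cycle 1 is missed.

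**The case against.** The strongest reply is that the documents give no non-completion rate, reasons or outcomes. Many missed day 15 doses may be holds for transient neutropenia: Section 2.1.2.5 reports grade 4 or worse in 57.7% of patients, often lasting under 5 days. Such patients need not fail at 4 months. If a held dose counts as completed, few patients may be excluded. The alpha argument depends further on a benchmark source that cannot be checked here. Under convention A, which is closer to the text because 13.3 would not credit a non-completer with a success, alpha is often below 0.05 once g reaches 10%. Sections 11.1.1, 13 and 13.5.2 also suggest an intention to count early failures. Finally, this is a non-randomised phase II screen already under way, with 15 patients accrued by 5 December 2017.

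Much of this stands as a limit on size. The alpha rise is conditional, 0.120 should carry little weight, and the upward bias requires non-completers to do worse than completers. It does not remove the defect. Deaths and progressions before completing cycle 1 are certain failures on the primary endpoint, and 13.3 drops them. The passages suggesting otherwise do not override it, and the missing definition of completion adds to the problem.

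**Conclusion.** The concern holds and needs correcting. As written, 13.3 and 13.5.2 give the wrong denominator for the endpoint that decides whether an arm continues and succeeds, and remove early events from PFS and OS. That exclusion follows directly from the text. The bias is upward if non-completers do worse than completers: about 1 to 4 percentage points at a true 15%, and 2 to 10 at a true 40%, for q = 5 to 20% and g = 0.

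The alpha point is real but less certain. With the two spare places that remain if both open arms fill, alpha is 0.057 to 0.077 if all non-completers are failures and the 15% refers to all treated patients. It falls to 0.0497 or below if g is near 15% or if the benchmark describes completers. Both q and g are assumptions.

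**What to change.** In Sections 13, 13.3 and 13.5.2:

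- Define the primary efficacy set as all eligible patients who received at least one dose. Section 4.1 already cancels registrations with no treatment. Use the same set for PFS and OS.
- Count anyone not documented alive and progression-free at 4 months as a failure, in both the stage 1 and the final count.
- Do not let replacements for treated patients enter the decision counts.
- Keep cycle 1 completers as a labelled sensitivity analysis, and state how a held day 15 dose is classed for that analysis.
- State whether the 15% and 40% refer to all treated patients or to completers, and give the resulting power.
- Reconcile 11.1.1, 13, 13.2, 13.3 and 13.5.2.

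The cost is an amendment to Section 13, including its replacement rule, during accrual, and a somewhat less favourable reported rate. If 40% refers to all treated patients, power stays at 0.813. If it was meant for completers and non-completers count as failures, the all-treated rate is 0.40(1 − q) = 38/36/32% and power is 0.764/0.707/0.574 at q = 5/10/20%. That loss should be stated, or covered by the sample size.

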6.3.1 Dose Modifications

A maximum of two dose reductions are allowed. If a patient requires more than two dose reductions, they should be removed from the trial. Once a patient's dose has been reduced, it may be re-escalated to the previous dose level if the toxicity has resolved to baseline or \leq grade 1 and with agreement from the principal investigator.

Table 7: Dose Modifications	
Dose Reduction Level	Prexasertib Dose
-1	80 mg/m ²
-2	60 mg/m ²

If the study medication is placed on hold for toxicity, the counting of cycle days and assessment schedule will continue without interruption. For example, a patient who does not receive their prexasertib (LY2606368) infusion on cycle 2 day 15 due to toxicity will proceed with their next scheduled visit as previously planned (cycle 3 day 1) with additional interim visits as needed for clinical management. The cycle will not restart for dosing delays due to toxicity.

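### The go/no-go rule is stated over patients enrolled but the analysis keeps only eligible cycle 1 completers, so the stated 80% power is not secured and early failures leave the denominator

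*Combined protocol and SAP*

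**What the plan says.** Section 13 describes a Simon two-stage design for each arm. Nine participants are enrolled and the arm stops if fewer than 2 are alive and progression-free at 4 months; otherwise it grows to 19. The final criterion is "A minimum of 6 patients must be alive and progression-free at 4 months for the cohort to be considered meaningful for further evaluation". The stated properties are 80% power at 40% against a historical rate of 15% or less, at one-sided 0.05. The rule carries no evaluability condition, and the same section adds "Progression status by 4 months will be determined for all patients".

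The sentence after the rule allows replacement: a participant who "does not complete Cycle 1 dosing of the study agent, that participant may be replaced", at the principal investigator's discretion.

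Section 13.3 then defines the analysis set: "The primary and secondary analyses will include all eligible patients who completed at least one cycle of dosing". Section 13.5.2, on the primary efficacy endpoint, repeats that restriction, yet its outcome categories include early death from disease, toxicity or other cause. Section 11.1.1 treats objective progression before the end of cycle 1 as evaluable for response. Section 1.2 states the objective as a proportion of patients in the cohorts, with no reference to completing a cycle.

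Section 13.2 gives a maximum of 19 per arm. It then allows for replacement: "the estimate for the maximum sample size is 50 participants".

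**The concern.** Alpha and power in section 13 are properties of exactly 9 and 19 counted patients. The plan does not say which patients the cut-offs of 2 and 6 apply to, and it does not hold the section 13.3 set at those numbers. A non-completer need not be replaced, and replacement is offered only for incomplete cycle 1 dosing although section 13.3 also removes ineligible patients. No cut-off is given for any other number.

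Completing a cycle of dosing is also undefined. Section 6.3.1 keeps the calendar running when a dose is held: "The cycle will not restart for dosing delays due to toxicity". Its example is cycle 2 day 15, but the same logic could apply to cycle 1 day 15. A patient still on treatment and progression-free might then be classed as not having completed cycle 1.

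The second problem is who is removed. A patient who dies or progresses during cycle 1 has failed the primary endpoint, yet section 13.3 can take that patient out of the denominator. That conflicts with section 11.1.1 and with the early-death categories in section 13.5.2. At stake are the stated power and, if early failures are replaced by other patients, the meaning of the 15% benchmark.

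**Working it through.** **Inputs.** From section 13: n1 = 9, continue at 2 or more; n = 19, success at 6 or more; null 15%, alternative 40%, one-sided 0.05. The non-completion share d is assumed at 5% and 10%.

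**Formula.** Pr(success) = sum over x = 2 to n1 of b(x; n1, p) × P[Bin(n − n1, p) ≥ 6 − x], where b is the binomial probability.

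**The plan's own figures (n1 = 9, n = 19).** Terms for x = 2, 3, 4, 5 and 6 or more:
- p = 0.15: 0.01298 + 0.01922 + 0.01290 + 0.00401 + 0.00063 = 0.0497.
- p = 0.40: 0.09960 + 0.20886 + 0.23920 + 0.16620 + 0.09935 = 0.813.

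The stated 5% and 80% are reproduced, with almost no slack on alpha.

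**Other counted totals, cut-offs kept at 2 and 6, 9 in stage 1.** Counted patients are taken to share the same success rate.

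| Counted total | Alpha at 15% | Power at 40% |
|---|---|---|
| 17 | 0.031 | 72.5% |
| 18 | 0.040 | 77.4% |
| 19 | 0.0497 | 81.3% |
| 20 | 0.061 | 84.4% |

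If the shortfall is in stage 1, 8 then 18 counted gives power 75.6%. The chance of stopping wrongly at a true 40% is 0.6^8 + 8 × 0.4 × 0.6^7 = 10.6%, against 0.6^9 + 9 × 0.4 × 0.6^8 = 7.1% with nine.

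**Effect of leaving early failures out.** Suppose every non-completer fails and is replaced, so that 9 and 19 completers are counted. An all-patient rate of 15% becomes 0.15/(1 − d) among completers.
- d = 5%: 0.15/0.95 = 15.8%; alpha of the 9/19 rule 6.2%.
- d = 10%: 0.15/0.90 = 16.7%; alpha 7.7%.

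If those patients were not replaced, the number of successes would be the same as with them counted as failures, and alpha against an all-patient 15% would stay at 4.97%. The inflation therefore comes from replacing failures.

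**Counting non-completers as failures within 9/19.** If 40% was meant for completers and no non-completer succeeds, the rate is 0.40 × (1 − d).
- d = 5%: 38%; power 76.4%.
- d = 10%: 36%; power 70.7%.

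If 40% was meant for all patients, power is 81.3%.

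**Cut-offs for other totals (9 in stage 1, alpha at most 0.05).** Requiring 5 at n = 15 gives alpha 0.0594, so 6 is needed from 15 to 19. Requiring 7 gives 0.0209, 0.0269, 0.0338 and 0.0416 at n = 20, 21, 22 and 23.

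**The case against.** The strongest reply is that the two sets are really one. The replacement sentence directly follows the rule, a replaced participant ordinarily gives up the place, and section 13.2 sets 19 per arm before allowing a larger total for replacements. On that reading the 9 and 19 are completers, as sections 13.3 and 13.5.2 say, and the sentence on progression status for all patients concerns data completeness. Eligibility is checked before registration (section 4.1), so later exclusions should be few.

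Most of this stands, and it is the most natural reading. It restores 9 and 19 only if every non-completer is replaced and nobody is found ineligible. The plan makes the first discretionary and does not provide for the second. The reading also does nothing about early failures leaving the denominator.

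It does rule out several stronger inferences that a reader might draw:
- *That alpha exceeds 5% because too many are counted.* The 6.1% at 20 arises only if a replaced patient and the replacement are both counted.
- *That one arm will both pass and fail.* This would need a patient to be replaced at discretion and then be progression-free at 4 months. It is possible on the text but contrived.
- *That only two replacements are available.* The arithmetic is 50 − 10 − 19 − 19 = 2, but section 13.2 calls 50 an estimate, and an arm that stops at stage 1 frees its places. No power figure should rest on 50 as a hard limit.
- *That the closed arm is compromised.* Section 13.2 says "The replicative stress cohort is now closed and will not expand, having enrolled 10 participants". Ten against nine fits one replacement, and no 6-of-19 decision remains there.

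**Conclusion.** The point holds in limited form. The design is valid at exactly 9 and 19, but the analysis set and optional replacement do not secure those numbers. One patient short in stage 2 takes power from 81.3% to 77.4%, and two short to 72.5%. These figures assume that the cut-offs stay at 2 and 6 and that counted patients have the 40% rate. On the natural reading a shortfall in numbers lowers alpha, so the loss there is power.

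Separately, replacing early failures raises the one-sided error to 6.2% or 7.7% against an all-patient rate of 15%. This rests on assumed non-completion of 5% or 10%, on every non-completer failing, and on 15% referring to all patients. If 15% was meant for completers, this inflation does not arise; section 13 does not say which population it describes. The documents do not support a claim that the trial's error rates have already failed. They do support asking for one defined, fixed-size set while patients remain to be enrolled: section 13.2 puts this at 35 as of 5 December 2017.

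**What to change.** Use one set for the rule in section 13 and for the estimate in sections 13.3 and 13.5.2: the first 9 and first 19 patients per arm who are eligible and receive any prexasertib. Count anyone not documented alive and progression-free at 4 months as a failure, and remove discretionary replacement for efficacy. This matches the objective in section 1.2 and keeps 2 of 9 and 6 of 19 exact.

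State the cut-off in case the counted total still differs (with 9 in stage 1: 6 for 15 to 19, 7 for 20 to 23). Report the proportion with an exact interval that allows for the two stages. Report the closed replicative stress arm descriptively.

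The cost is a few sentences and no extra patients: 10 + 19 + 19 = 48, plus any treated patient later found ineligible, against the present estimate of 50. The downside is power if 40% was meant for completers only and no non-completer succeeds: 76.4% or 70.7% at 5% or 10% non-completion, and the power statement should then be revised. If 40% was meant for all patients, as section 1.2 reads, power remains 81.3%. The sponsor should say which was intended.

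### Does the lack of a named interval or p-value method for the two-stage 4-month progression-free rate undermine the 6-of-19 success rule?

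*Combined protocol and SAP*

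**What the plan says.** Section 13 sets out the test in full. "Each arm will be conducted as a Simon's 2-stage design and will initially enroll 9 participants". The stopping clause reads "If there are less than 2 subjects that are alive and progression-free at 4 months"; otherwise "enrollment for that arm will be expanded to 19 subjects". The success criterion is a count: "A minimum of 6 patients must be alive and progression-free at 4 months for the cohort to be considered meaningful for further evaluation". The operating characteristics given are 80% power at a true rate of 40% against a historical rate of at most 15%, "using a one-sided significance of 0.05".

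Section 13.3 then describes the analysis of this endpoint in one clause: "Progression-free rate will be estimated as binomial proportion". Nothing in sections 13 to 13.5 adds an interval, a confidence level or a p-value method for the 4-month rate.

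Two further statements bear on the denominators. Under section 13, if a participant does not complete Cycle 1 dosing, "that participant may be replaced at the principal" investigator's discretion. Section 13.2 says "The replicative stress cohort is now closed and will not expand, having enrolled 10 participants".

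**The concern.** The design section is written as a hypothesis test with a one-sided alpha, while the analysis section offers only a point estimate. A reader would expect a matching interval. The natural default, a Clopper-Pearson interval that treats the 19 patients as one fixed sample, ignores the stop after 9.

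That matters at the success threshold. The rule of at least 6 of 19 meets one-sided 0.05 only because arms with fewer than 2 of 9 have already stopped. Without the stop, the same count gives 0.0537. An arm with exactly 6 of 19 could therefore be declared promising beside an interval that still contains the historical rate. Because no method is named, the interval could also be picked once the result is known. Among arms that succeed, 6/19 is a frequent result when the drug is weak: 68% of successes at a true rate of 15% and 57% at 20%.

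**Working it through.** **Inputs (section 13).** Stage 1 n = 9; stop if at most 1 success; total n = 19, so 10 in stage 2; success if the total is at least 6; null rate 0.15; target rate 0.40.

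**Step 1: reproduce the plan's own figures.** With x the stage 1 count,

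P(success | p) = Σ over x = 2..9 of P(Bin(9,p) = x) × P(Bin(10,p) ≥ 6 − x).

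| x | p = 0.15 | p = 0.40 |
|---|---|---|
| 2 | 0.25967 × 0.04997 = 0.01298 | 0.16124 × 0.61772 = 0.09960 |
| 3 | 0.10692 × 0.17980 = 0.01922 | 0.25082 × 0.83271 = 0.20886 |
| 4 | 0.02830 × 0.45570 = 0.01290 | 0.25082 × 0.95364 = 0.23920 |
| 5 | 0.00499 × 0.80313 = 0.00401 | 0.16722 × 0.99395 = 0.16620 |
| 6 to 9 | 0.00063 | 0.09935 |
| Sum | **0.0497** | **0.8132** |

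The count rule has type I error 0.0497, under the 0.05 ceiling, and power 81.3% against the stated 80%. The test is as described.

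**Step 2: the fixed-sample figure at 6/19.** P(Bin(19, 0.15) ≥ 6) = 0.0537. The excess over 0.0497 is the contribution of arms that would have stopped: 0.23162 × 0.00138 (x = 0) + 0.36786 × 0.00987 (x = 1) = 0.0003 + 0.0036 = 0.0040.

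**Step 3: intervals at 6/19 = 31.6%.** The two-stage limits come from inverting the tail probabilities of the Step 1 sum.

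| Method | Level (two-sided) | Lower limit | Excludes 15%? |
|---|---|---|---|
| Clopper-Pearson, fixed sample | 90% | 14.75% | No |
| Two-stage | 90% | 15.02% | Yes |
| Wilson | 90% | 17.3% | Yes |
| Wald | 90% | 14.0% | No |
| Clopper-Pearson, fixed sample | 95% | 12.6% | No |
| Two-stage | 95% | 12.8% | No |

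The 90% rows correspond to the one-sided 0.05 test. There, the fixed-sample exact limit misses 15% by 15.00 − 14.75 = 0.25 points. The 95% rows correspond to one-sided 0.025, a level the plan does not claim, so their including 15% is no contradiction.

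**Step 4: how far it extends.** At 7/19 the p-values are 0.0163 (fixed sample) and 0.0158 (two-stage), and the 90% lower limits are 18.75% and 18.87%. The mismatch is gone.

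**Step 5: how often it can arise.** P(continue and finish with exactly 6) = Σ over x = 2..6 of P(Bin(9,p) = x) × P(Bin(10,p) = 6 − x).

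| True rate | P(exactly 6/19) | P(success) | Share of successes |
|---|---|---|---|
| 15% | 0.034 | 0.050 | 68% |
| 20% | 0.087 | 0.152 | 57% |
| 30% | 0.174 | 0.501 | 35% |
| 40% | 0.132 | 0.813 | 16% |

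The 68% is a share of an event that itself has a 5% chance. Unconditionally, the outcome has probability 3.4% at the null and never exceeds 17.4% at these four rates.

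**Step 6: does a two-stage p-value guarantee agreement?** Only if exactly 9 + 10 patients are analysed. With six successes and the same stop rule, it is 0.0516 for 10 + 9, 0.0608 for 9 + 11 and 0.0397 for 9 + 9.

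**The case for a change.** The best argument for amending section 13.3 is that a rate from 19 patients will be published, a reader needs its uncertainty, and agreement between interval and success rule at 6/19 turns on an unstated choice. Clopper-Pearson and Wald at 90% include 15%; Wilson and the two-stage interval do not. One sentence naming a method and level would settle this at negligible cost. Replacement and the one-cycle requirement also make analysed sizes other than 9 and 10 plausible, and the plan does not say what happens then.

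The omission stands as a fact, and so does the dependence on method at 6/19. The rest does not amount to a defect. The test is already prespecified as a count, so an interval chosen late cannot turn a failed arm into a success or the reverse. The two-stage allowance is not missing either: it is built into the stop and success counts, where it affects the decision. A two-stage p-value would not reliably remove the mismatch, because Step 6 shows it can itself pass 0.05 at six successes when the sizes drift. The choice of denominator is a separate question from the choice of interval. The replicative stress arm, closed after 10, never reaches a 19-patient assessment, so the point cannot arise there.

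**Conclusion.** No change to the plan follows. Carried out as written, it gives a valid decision (type I error 0.0497, power 0.813) and a raw proportion. The apparent conflict needs an added interval that the plan does not mention. With the exact fixed-sample form at the matching 90% level, it arises at the single outcome 6/19, where the lower limit is 14.75% instead of 15.02%. Under either method a colleague would read that result as borderline.

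An analyst who wants an interval can fill the gap sensibly: a 90% two-sided interval from the two-stage sampling distribution agrees with the count rule at 6/19, and the count rule remains the decision. All these figures assume 9 and 10 patients analysed in an arm that expands.
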